11.4 Vital Signs

Descriptive summaries (mean, SD, median, minimum, and maximum) of actual values and changes from baseline at each assessment time point and last available assessment will be calculated for vital signs including weight, BMI, body temperature, pulse rate, systolic blood pressure and diastolic blood pressure. 95% confidence intervals will be presented for change from baseline.

These summaries will be presented by treatment and assessment time for the Safety population. ET data will be analyzed with the closest visit that does not have a valid assessment value.

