- ^d Clinical laboratory tests (hematology and serum biochemistry) will be performed at Screening and Week 14/ET. For patients where a telephone visit is being conducted for Week 14/ET, the laboratory tests will not be required. TSH will be tested at Screening only. Optional HCV/HBsAg testing may be performed at Screening at the discretion of the Investigator or Sponsor. Medical Monitor approval is required prior to testing.
- ^e A serum pregnancy test will be performed at Screening, followed by in-clinic urine pregnancy tests at Baseline, Week 2, Week 6, Week 10 and Week 14/ET for women of child-bearing potential. For patients where a telephone visit is being conducted, the urine pregnancy test will be performed at home by patient for women of child-bearing potential.
- ^f Vital signs (oral temperature, weight and sitting blood pressure and heart rate [obtained after resting for 5 minutes in a sitting position]) will be measured at each visit. Height will be measured at Screening only. For patients where a telephone visit is being conducted, the vital signs will not be required.
- ^g A 12-lead electrocardiogram will be obtained at Screening. All electrocardiograms will be performed and interpreted locally.
- ^h Clinic staff members will train the patient on how to take the study drug and how to complete the diary. Patients will be asked to complete their diary every evening. Diary completion will start on the evening of Visit 1 and continue through Week 14. Diary responses will be monitored during the study.
- ⁱ The study drug will be dispensed to patients at Baseline on Day 1 (following randomization) and at Weeks 2, 6, and 10. One bottle will be dispensed on Day 1 and two bottles will be dispensed at Weeks 2, 6 and 10. For patients where a telephone visit is being conducted, the study drug will be mailed via courier to their home. Patients will be instructed to take one tablet of study drug sublingually every evening at bedtime for 2 weeks starting the evening of Day 1, and then 2 tablets sublingually every evening from Week 2 to Week 14.
- ^j Patients will assess their average daily pain over the last 24 hours every evening using an 11-point (0-10) numerical rating scale. Patients should be instructed to complete their diary responses in the evening, but before taking their bedtime dose of study drug. The 24-hour recall interval will assess the previous night's sleep and symptoms of pain since bedtime the previous night.

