5.4. Conclusion for Study Design

[REDACTED]

The present study is a Phase 3, randomized, double-blind, multicenter trial designed to evaluate the efficacy and safety of TNX-102 SL 5.6 mg (2 x 2.8 mg tablets) taken once daily at bedtime compared to placebo over 14 weeks in patients with fibromyalgia. Since fibromyalgia patients are often quite sensitive to medication side effects, the protocol includes a 2 week dose titration starting at 2.8 mg dose, followed by an increase to 5.6 mg from Day 15 through end of study. Additionally, to mitigate the potential for discontinuations due to tolerability at 5.6 mg in the FM population, the protocol includes a provision for the Investigator to reduce the dose back to one tablet daily at bedtime, either temporarily, or for the duration of the study, in order to prevent missing data due to AE-related discontinuations. Even so, the goal and design of the study is to always encourage the continued dosing with TNX-102 SL 5.6 mg nightly after the initial 2-week dose titration phase, and it is anticipated that dose lowering will only rarely be necessary in the study.

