13. STATISTICAL CONSIDERATIONS AND ANALYSES

A complete description of the statistical analyses to be performed will be provided in the study-specific SAP, which will be finalized prior to database lock and the unblinding of study treatments.

Baseline will be defined as those values recorded closest to, but prior to administration of the first dose of study drug.

Unless otherwise noted, significance tests of treatment differences will be tested at the two-sided 0.05 level.

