Descriptive summaries (mean, SD, median, minimum, and maximum) of actual values and changes from baseline at each assessment time point and last on-treatment assessment will be calculated for vital signs including weight, BMI, body temperature, pulse rate, systolic blood pressure and diastolic blood pressure. 95% confidence intervals will be presented for change from baseline.

Based on the C-SSRS results, the overall number of patients with lifetime and/or current suicidal ideation (by item and category), suicidal behavior (by item and category), or self-injurious behavior at the screening and baseline visit will be summarized by visit and treatment group. Additionally, the overall number of patients with any suicidal ideation or behavior (by type and in total) or self-injurious behavior while on-treatment will be provided by treatment group. Patients will only be counted once for on-treatment at the worst-case response for each item.

Physical examination data and oral examination data will be presented in data listings.

Descriptive summaries (mean, SD, median, minimum, and maximum) of actual values and changes from baseline at each assessment time point and last on-treatment assessment will be calculated for BDI-II scores. 95% confidence intervals will be presented for change from baseline.

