8. GENERAL ISSUES FOR STATISTICAL ANALYSIS

8.1 General Statistical Methodology

Descriptive summaries will be provided where appropriate for each of the primary and secondary variables. In general, tables will summarize data by treatment group and visit. All subjects for a population in each treatment group will be grouped together; subjects that reduce dose from two tablets per day to one tablet per day will not be reported separately for the analyses described in this SAP, unless otherwise noted. If there are more than 10 subjects in the active arm with a dose reduction at any point in the study, summary statistics on key outcomes may be reported for subjects with dose reductions.

Baseline characteristic and safety tables will be completed for the Safety Population unless otherwise specified. Efficacy tables will be presented for the ITT Population.

Continuous, quantitative variable summaries will include the number of subjects (N) with non-missing values, mean, standard deviation, median, minimum, and maximum.

Categorical, qualitative variable summaries will include the frequency and percentage of subjects who are in the particular category. In general, the denominator for the percentage calculation will be based upon the total number of subjects in the study population for the treatment group unless otherwise specified.

Baseline values are defined as the last non-missing measurement prior to the first dose of study drug. For scores obtained via diary, baseline will be defined as the average of the scores from the 7 days prior to the baseline visit. Change from baseline will be defined as the post-baseline visit value minus the baseline value.

Study day is defined as assessment date – first dose date +1.

All analyses will be performed using SAS[®] Software version 9.3 or later.

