11.2 Clinical Laboratory Evaluations

Laboratory data (analytes for Chemistry and Hematology) will be summarized by treatment and visit for the Safety Population. Descriptive summaries of actual values and changes from baseline will be presented by study visit and last available assessment for each clinical laboratory analyte and each treatment group. 95% confidence intervals will be presented for change from baseline. ET data will be analyzed with the closest visit that does not have a valid assessment value.

Laboratory values will be displayed in the data listings with their corresponding normal ranges, and those values that are outside the normal range will be flagged. For each laboratory analyte, shifts in assessments of abnormality from baseline to each scheduled time point will be presented in shift tables.

A by-subject listing of all clinical laboratory (Chemistry, Hematology and Urinalysis) data will

also be provided.

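### For laboratory values, vital signs and BDI-II the only planned intervals are for change from baseline; no interval is planned for TNX-102 SL minus placebo

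*SAP*

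**What the plan says.** Protocol 5.4 describes a trial of the efficacy and safety of the 5.6 mg dose "taken once daily at bedtime compared to placebo over 14 weeks in patients with fibromyalgia". For three kinds of continuous safety data, the planned outputs are as follows.

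- **Vital signs (SAP 11.4):** "95% confidence intervals will be presented for change from baseline", and "These summaries will be presented by treatment and assessment time for the Safety population".
- **Laboratory values (SAP 11.2):** actual values and changes are "presented by study visit and last available assessment for each clinical laboratory analyte and each treatment group. 95% confidence intervals will be presented for change" (meaning change relative to the baseline value). Shift tables and out-of-range flags are added.
- **BDI-II (Protocol 13.5 only):** summaries "will be calculated for BDI-II scores. 95% confidence intervals will be presented for change from baseline". SAP section 11 lists BDI-II among the safety data but has no subsection for it. The protocol sentence does not mention the split by arm.

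SAP 8.1 defines the quantity: "Change from baseline will be defined as the post-baseline visit value minus the baseline value". There is no placebo term. Neither document plans a treatment difference, a model or a between-arm interval for these three data types.

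One safety-related outcome is handled differently. SAP 10.3 analyses CSFQ-14, which it describes as supporting the product's safety, by ANCOVA with treatment, site and baseline, and reports 95% CIs.

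**The concern.** An interval for mean change within one arm has zero change as its reference, and it makes no use of the concurrent placebo group. Zero is a doubtful reference here, because the design gives reasons for both arms to move together.

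- **BDI-II:** Protocol 8.3 excludes scores above 24 at Screening or Baseline. Cutting off the top of the distribution at entry makes later scores tend to rise in both arms.
- **Laboratory values:** Protocol Table 2, footnote d: "Clinical laboratory tests (hematology and serum biochemistry) will be performed at Screening and Week 14/ET". In patients who wash out an excluded drug, the scheduled laboratory baseline therefore precedes the washout, and the change carries the washout as well as the study drug. The AST/ALT entry limit of twice the upper limit of normal also truncates the baseline.
- **Placebo response:** this may move BDI-II in both arms, probably opposite to the regression above.

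The placebo arm removes such shared movement only if the two arms are contrasted. Without that contrast, shared drift can look like a drug effect in the active column, and a shared change in the favourable direction can offset an adverse one. The package insert appended to the protocol lists tachycardia, changes in blood pressure, weight gain or loss, abnormal liver function and depressed mood. These are matters that the three data types are meant to pick up.

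**Working it through.** **Inputs from the documents.** There are 470 patients at 1:1, so 470/2 = 235 per arm (SAP 6). The confidence level is 95%, two-sided. The plan states no figure to reproduce on this point, and the assumptions behind the sample size are redacted.

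**Assumptions.** Drift and harm are in units of the SD of change, because no SD is given. Evaluable patients per arm: 200, with a range of 165 to 235 (30% to 0% missing). Telephone visits omit vital signs and laboratory tests, so some loss is likely.

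**Formulas (normal approximation).**
- Within-arm half-width = 1.96/√n
- Between-arm half-width = 1.96·√(2/n)
- P(within-arm CI excludes 0) = Φ(d√n − 1.96) + Φ(−d√n − 1.96), for mean change d
- P(between-arm CI excludes 0): the same expression, with δ/√(2/n) in place of d√n, for difference δ

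**Half-widths at n = 200.** Within-arm 1.96/14.14 = 0.139 SD. Between-arm 1.96 × 0.1 = 0.196 SD.

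**Step 1: equal drift in both arms, no drug effect, n = 200.**

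| Shared drift (SD) | d√n | Active-arm CI excludes 0 (exact t) | Between-arm CI excludes 0 |
|---|---|---|---|
| 0.10 | 1.41 | 29% | 5% |
| 0.15 | 2.12 | 56% | 5% |
| 0.20 | 2.83 | 80% | 5% |

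At 0.20 SD the active-arm figure runs from about 72% (n = 165) to 86% (n = 235).

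**Step 2: comparing the two arms' intervals by eye.** With equal drift of 0.13 SD and n = 235, each interval excludes zero with probability p = 0.51. Exactly one of the two does so with probability 2p(1 − p) = 2 × 0.51 × 0.49 = 50%. In half of such trials the columns look different although the drug does nothing.

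**Step 3: opposite drift.** Take a harm of 0.30 SD and a shared drift of −0.30 SD, n = 200. The net active-arm change is 0, so its interval excludes zero in 5% of trials. For the difference, 0.30/0.1 = 3, and Φ(3 − 1.96) = 85%. Exact cancellation is the extreme case.

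**Step 4: BDI-II cap alone, by simulation.** Assumed: SD 9, retest correlation 0.70 to 0.85, 200 per arm, both pre-treatment scores at most 24, no drug effect. The active-arm interval excludes zero in about 10% to 39% of trials for uncapped means of 14 to 18, and in about 7% to 8% for a mean of 10. The between-arm figure is about 5%. The drift is about 0.2 to 0.8 points for means of 14 to 18. The effect is therefore modest and depends on the unknown baseline mean.

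**The case against.** The strongest reply is that these outputs are descriptive and nothing is decided on them. A reader might infer that the plan tests safety against the wrong null. The documents do not support that. Protocol 13 sets a level for tests, "significance tests of treatment differences will be tested at the two-sided 0.05 level", but no such difference is defined for these data, and formal inference is confined to the primary and key secondary endpoints. No rule says that an interval excluding zero means a drug effect. The percentages above describe how often an interval could mislead a reader who looks at the active arm alone; they are not error rates of a planned test.

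A reader might also infer that real harm will be hidden. That goes too far. Laboratory and vital-sign results appear by arm, and SAP 8.1 requires N, mean and SD, so an unadjusted difference and its interval can be worked out from the table. Laboratory shift tables, adverse event tables and C-SSRS summaries give further cover. What stands is that none of these outputs carries a between-arm interval.

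Two broader readings also fail. It is not true of every continuous safety-related measure, because CSFQ-14 gets a between-arm ANCOVA. Nor does every laboratory change mix washout with study drug. Some patients need no washout, and vital signs and BDI-II are measured again at Visit 2, after any washout.

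**Conclusion.** The gap is real: no drug-placebo interval is planned for laboratory values, vital signs or BDI-II, although comparison with placebo is the stated purpose. The within-arm intervals can mislead in either direction when both arms move.

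The size depends on assumed drift. At 0.10 to 0.20 SD and 200 per arm, the active-arm interval excludes zero in about 29% to 80% of trials with no drug effect, against 5% for the contrast. With little drift the problem is small, as the BDI-II result at a mean of 10 shows. This is a weakness in safety reporting and a cheap improvement. It does not touch the primary result, error control or data collection.

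**What to change.** Keep the within-arm summaries and their intervals. Add to SAP 11.2, SAP 11.4, a new SAP subsection for BDI-II, and Protocol 13.5 wording such as:

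*The baseline-adjusted difference between TNX-102 SL and placebo in mean change will be presented with a 95% CI, from an ANCOVA with treatment and baseline value, at Week 14 and at the last assessment, and for vital signs and BDI-II at each post-baseline visit. Skewed analytes will be analysed on the log scale or by a robust method. These intervals are descriptive and are not adjusted for multiplicity.*

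The model follows the one already planned for CSFQ-14, which also includes site.

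The cost is wording and some table programming; no new data or patients are needed. The downside is chance findings. Protocol Table 3 has about 38 routine chemistry and hematology measures, so about 38 × 0.05 = 1.9 intervals would be expected to exclude zero at one time point with no drug effect. The descriptive label is there for that reason.

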11.5 Physical Examination and Oral Cavity Exam

A standard physical examination will be performed at Screening, Baseline, and Week 14. In addition, a separate examination of the oral cavity will be performed at each visit (Screening through Week 14). Oral cavity examination findings will be documented separately from other physical examination findings.

A data listing of the results at each scheduled visit will be presented for both the standard physical examination and the examination of the oral cavity.

12. MEDICATIONS

12.1 Concomitant Medication

All medications will be coded using the World Health Organization Drug Dictionary (WHO-DD Version 2019-Sep). Prior and concomitant medications will be summarized by treatment group and by the number and percentage of subjects taking each medication, classified by using WHO-DD Anatomical Therapeutic Chemical Levels 1 and 3 and preferred term.

Prior medications are defined as medications or therapies initiated prior to the start of the study drug and terminated prior to the start of study drug. Hence, these medications or therapies will have end dates prior to the first dose date of study drug. Concomitant medications are defined as any medications other than the study drug that a subject receives concurrently with the study drug. These medications will have end dates on or after the first dose date of the study drug.

Prior and Concomitant medications will be summarized. All medications will be presented in a listing.

Please refer to [Section 8.3](#) to impute the partial start date and end date of concomitant medication.

12.2 Opioid Medications

A list of subjects' concomitant medication records from the CRF data identifying opioid usage will be reviewed by the project team and approved by the sponsor prior to database lock. This listing will be used to flag opioid records in the analysis database and in the by- subject concomitant medication listings.

12.3 Exposure and Compliance

The treatment duration will be calculated and summarized based primarily on CRF data for first and last dose dates (number of days=last dose date - first dose date+1). If these values are missing or subjects' diary data indicate dates that exceed this period, the diary dates will be utilized.

Days of exposure will be based on subjects' responses to the daily questions regarding medication usage. The number of days on study drug is the total number of days a subject respond that study drug was taken. If the CRF data for the last dose date is a date not included in the diary, it will be added to the count (this should be true for most completing subjects since they do not fill out a diary the day of their last visit). The number of subjects with total exposure by visit weeks (≤ 2 weeks, 2 to ≤ 4 , 4 to ≤ 8 , 8 to ≤ 12 , 12 to ≤ 14 and >14 weeks) will be presented. Missing days where the subject did not complete the diary will be treated as though study drug was not taken. Days of exposure will also be calculated for the days on each dose of study drug.

Additionally, the number and percentage of subjects that drop back to one tablet per day will be summarized and the week in which they reduced their dose will be tabulated (among those that had a dose reduction).

Compliance will be similarly summarized across all study visits for each treatment arm. Study drug compliance as a percentage will be defined as the exposure days defined above divided by the total number of expected days on treatment multiplied by 100. The expected number of days will be the date of last diary recorded dose-randomization date +1. This compliance reporting

will take into account whether or not they took any medication, but will not account for the number of tablets they took on a given day.

Compliance will be summarized with descriptive statistics by treatment arm. The number and percentages of subjects within certain categories of compliance (e.g. < 60%, 60% to < 80%, 80% to <= 100%, greater than 100%) will also be presented.

A listing of drug accountability data based on CRF data will be provided.

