10.5. Study Drug Accountability and Reconciliation

All patients will be expected to bring their bottles of study drug with them to all study visits (including empty bottles), unless a telephone visit, where patients will be asked to count the number of tablets remaining in their current bottles, document this on a form provided to patient, and return this form and study drug (with bottles) via courier to the site. At each study visit, the site staff will inspect the drug bottles, and perform a count of the tablets remaining in the bottles and document this in the patient's record. For telephone visits, drug accountability by the site staff will occur after the study drug is returned to the site via courier. For home visits (Week 14 or ET only), site staff will collect bottles and conduct accountability upon return to the site. An assessment of drug adherence should be done by the study staff to ensure that the patient understands all dosing instructions and is taking the drug as prescribed. Patients will be asked for an explanation if the count of returned study drug tablets indicates a discrepancy between the expected number of tablets dosed and the number returned in the bottles. If it is found that the patient is not taking the study drug as expected, the patient will be re-counseled with instructions, and this should be noted in the patients' records. A deviation should be recorded on any patient who is less than 70% compliant with dosing between visits and one of the Medical Monitors should be contacted.

Tonix or its designee will perform drug accountability which entails reconciliation between the amount of drug shipped to the study site, study drug assigned and dispensed to the patient (including returned unused assigned study drug), and study supplies that were never dispensed and/or assigned to patients.

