12.2.6. Diary Assessments

The daily diary is an important aspect of this study, and all patients must receive training explaining what is being asked of them, when to complete the diary, and how to use the diary system effectively. Patients will need to receive instructions and a password that uniquely identifies them when they log into the system along with instructions about what to do if they have difficulty completing the diary.

The diary should be started the evening of Visit 1 and completed daily until Visit 6 (Week 14). Patients should be instructed to complete the diary in the evening before dosing. Once the patient has properly identified themselves, the diary will prompt answers to the following:

- Rate your average pain during the past 24 hours on a scale from 0-10, where zero is no pain and 10 is worst possible pain.
- Rate your sleep quality last night on a scale from 0-10 where 0 is the best possible sleep and 10 is the worst possible sleep.

After randomization to study drug at Visit 2, the following questions will be added to the daily diary (starting in the evening of the day after randomization, Day 2):

- Did you take your study drug last night? (Yes/No)
- If yes, how many tablets of study drug did you take last night? (1 tablet/2 tablets)

The study staff will be expected to monitor patient adherence in completing the diary throughout the study, and will be instructed to call the patient should any problems or significant non-adherence be observed. During the screening period, there are diary compliance requirements that must be met in order for the patient to qualify for randomization. Patients who have been randomized should be encouraged to continue to complete their diary. Patients will receive a reminder to complete their diary if they miss diary entries. Patients who miss two diary entries will be flagged by the IRT system, and site staff will be alerted to contact patients for re-training and to instruct the patient on the importance of routine completion of their diary.

12.2.7. Assessment of Changes in Sexual Function: Changes in Sexual Functioning Questionnaire Short-Form (CSFQ-14)

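### SAP compliance formula: the numerator can include a final CRF dose that the denominator leaves out, so a perfect completer scores 98/97 = 101.0%

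*SAP*

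**What the plan says.** SAP section 12.3 defines compliance as "the exposure days defined above divided by the total number of expected days on treatment multiplied by 100".

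- **Numerator, diary part:** "The number of days on study drug is the total number of days a subject respond that study drug was taken".
- **Numerator, CRF part:** "If the CRF data for the last dose date is a date not included in the diary, it will be added to the count". The SAP explains that "this should be true for most completing subjects since they do not fill out a diary the day of their last visit".
- **Denominator:** "The expected number of days will be the date of last diary recorded dose-randomization date +1".
- **Unanswered evenings:** "Missing days where the subject did not complete the diary will be treated as though study drug was not taken".

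The measure is yes or no per day and ignores the number of tablets. Results are summarised by arm and in example bands, one of which is for values above 100%. The SAP gives no worked compliance value, and no rule to cap the ratio or reconcile its two parts.

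The same section calculates treatment duration differently: last dose date minus first dose date plus 1, mainly from the CRF, with diary dates used if the CRF dates are missing or the diary extends further.

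**The concern.** The CRF dose is added to the numerator because the diary cannot capture the last night of dosing. The denominator still stops at the last dose that the diary did capture. Whenever the CRF day is added, the numerator can therefore exceed the denominator by one, and the SAP itself expects the addition to be routine among completers.

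What is at stake is how the compliance table reads. A value above 100% is usually taken to mean that more drug was used than prescribed. Here it cannot mean that, because a day counts at most once and tablets are ignored. The band would instead collect subjects with no recorded gap, and a completer with one missed dose would be reported as exactly 100%.

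**Working it through.** There is no stated compliance figure to reproduce, so this is a day count from the definitions.

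**Inputs**

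- Dosing runs from Day 1, the day of randomization, to Day 98 (SAP sections 4 and 4.2).
- The diary's dosing question concerns the previous night and first appears on Day 2 (Protocol section 12.2.6). An entry on day d therefore records the dose of day d − 1.
- With a Day 99 visit, the ideal last diary entry is on Day 98 (SAP section 8.2.1). SAP section 8.2.2 confirms the offset for the sleep question, whose last reported night is Day 97–98.

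**Timeline check.** The SAP's duration formula gives 98 − 1 + 1 = 98 dosing nights, which agrees with Days 1–98.

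**Perfect completer, Day 99 visit**

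- Diary entries on Days 2–98 record the doses of Days 1–97: 97 exposure days.
- The CRF last dose, Day 98, is not among them, so one is added: 98.
- Expected days: 97 − 1 + 1 = 97.
- Compliance: 98/97 = 101.03%.

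**General form.** Let L be the days from randomization to the last diary-recorded dose, inclusive, and g the missed or unanswered days within that span. When the CRF day is added, compliance = (L − g + 1)/L. This exceeds 100% only if g = 0 and equals 100% if g = 1. Without the CRF day it is (L − g)/L, which cannot exceed 100%. Only the added day can put anyone in the top band.

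| Case (all answered evenings accurate) | Numerator | Denominator | Compliance |
|---|---|---|---|
| Perfect completer, visit Day 95 | 94 | 93 | 101.08% |
| Perfect completer, visit Day 99 | 98 | 97 | 101.03% |
| Perfect completer, visit Day 106 | 105 | 104 | 100.96% |
| Visit Day 99, one dose missed before Day 97 | 97 | 97 | 100.0% |
| Fully adherent, early termination visit Day 71 | 70 | 69 | 101.45% |
| Fully adherent, early termination visit Day 43 | 42 | 41 | 102.44% |
| Fully adherent, early termination visit Day 24 | 23 | 22 | 104.55% |
| Fully adherent, early termination visit Day 15 | 14 | 13 | 107.69% |

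The early termination rows assume dosing up to the night before the visit, a last diary entry on that same day, and a last dose added from the CRF.

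**Other readings of the denominator date.** If dates mean diary entry dates throughout, Day 98 is already in the diary, nothing is added, and the perfect completer scores 97/98 = 98.98%. If the numerator uses dose dates and the denominator the entry date, the result is 98/98 = 100%. Only this mixed reading gives the right answer.

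**With one last-dose date in both parts.** Perfect completer: 98 − 1 + 1 = 98, so 98/98 = 100.0%. One missed dose: 97/98 = 98.98%. A fully adherent early terminator also scores 100%.

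**The case against.** The strongest objection is that this is a one-day wording mismatch in a descriptive table. That stands. The SAP defines no per-protocol population, efficacy is analysed in all randomized subjects, and no specified efficacy analysis uses compliance. Treatment duration, days on each dose and dose reductions are derived separately and do not use this denominator.

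It can also be said that the denominator was meant to end on the date of the last diary entry. The text refers to the date of a recorded dose, however, and the SAP's remark that most completers' last dose is absent from the diary makes sense only by dose date.

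Several stronger conclusions that a reader might infer are not supported:

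- **That the unanswered-evening rule is an error.** It is an explicit, conservative rule applied alike in both arms. Treating those evenings as missing would assume that adherence on them resembles adherence on answered days, which could inflate compliance. It also does not reach every gap, since evenings after the last diary-recorded dose leave the denominator. A subject whose last entry is Day 40, but who doses to Day 98, scores (39 + 1)/39 = 102.6%.
- **That skipping a fifth of the diary moves an adherent completer below 80%.** It gives (0.8 × 97 + 1)/97 = 81.0%. Twenty unanswered evenings give 78/97 = 80.4%; it takes 21 to cross, at 77/97 = 79.4%.
- **That anyone stopping on Day 10 scores 100%.** With three of ten doses missed, the tenth dose taken and the diary kept to Day 11, the score is 7/10 = 70%. A fully adherent subject whose last entry is Day 10, with the Day 10 dose added from the CRF, scores 10/9 = 111%. Early stopping is visible elsewhere, in the exposure bands of section 12.3 and the withdrawal tables of section 9.1.
- **That tablet counts go unused.** Site staff "perform a count of the tablets remaining in the bottles" at visits (Protocol section 10.5). The same section requires a deviation to be recorded below 70% compliance between visits, SAP section 9.2 summarises deviations by arm, and section 12.3 lists accountability data.
- **That the table misstates exposure to the studied dose.** Compliance ignores tablet number by design, so it is not the output that addresses dose.

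**Conclusion.** The mismatch is real but minor. As written, a perfect completer is reported at 98/97 = 101.0% and a completer with one dose missed before Day 97 at 100.0%. For completers the distortion is about 1 percentage point across the visit window. It grows as treatment shortens, reaching 107.7% for a fully adherent subject with a Day 15 termination visit. The band above 100% would hold subjects with no gap up to their last diary-recorded dose and a further dose added from the CRF, not subjects who took extra drug.

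This rests on reading the denominator date as the date of the dose, and on a CRF last dose one night after the last dose that the diary records. It affects the compliance table only, not exposure duration, any analysis population or any efficacy result.

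**What to change.** In SAP section 12.3, define expected days as last dose date minus first dose date plus 1, where the last dose date is the later of the CRF and diary dates. This is in substance the formula already used there for treatment duration. State that dates are dates of dosing, not of diary entry. Both parts of the ratio then end on the same day, and the band above 100% should be empty, so any entry in it becomes a data query.

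The cost is one or two sentences of SAP text and a small programming change before database lock, with no new data.

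Optionally, report the number of unanswered evenings beside compliance, or add a tablet-count summary from the accountability data. Neither is needed to correct the formula. Tablet counts have limits of their own, since SAP section 7 anticipates subjects who do not return all study drug.
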